4.2 Scientific Rationale for Study Design

This study seeks to evaluate whether an ultrasound-guided GNB can provide a clinically significant reduction in pain among patients suffering with acute or chronic knee, which in most cases will be attributed to knee OA. Knee OA is very prevalent, and flares of knee OA are a common reason why patients present to the ED, where patients typically receive oral, topical, or intravenous analgesics. However, these therapies are often ineffective for managing

breakthrough knee OA pain. Alternative analgesia strategies, such as the GNB, have shown efficacy in the rheumatology and orthopaedic literature for managing chronic knee OA pain. Development and implementation of safe alternative modes of analgesia may help to effectively manage breakthrough pain associated with knee OA without high doses of opioids or other potentially harmful non-opioid analgesics. Several isolated case reports have demonstrated success in the ED; however, comparative or randomized studies have not evaluated the utility of the GNB among ED patients who present with breakthrough knee OA pain.

4.3 Justification for Dose

For the GNB arm, the maximum recommended dosing for bupivacaine for regional anesthesia is 2.5 mg/kg. To minimize the risk of LAST, we will utilize weight-based dosing at 80% of the maximal safe dosing which will allow for effective and prolonged analgesia while minimizing the risk of complications and LAST. Patients with body mass index (BMI) greater than 25 kg/m^2 will receive a total of 80% of their ideal body weight dosing in bupivacaine. Patients with a BMI of equal to or less than 25 kg/m^2 will receive a total of 80% of their actual body weight dosing in bupivacaine. This total amount will be divided into three equal aliquots that will be injected around the three genicular nerves), which will be well below the recommended maximal dose for both female and male patients. Dexamethasone dosing ranging from 4-8 mg has shown to prolong regional anesthesia by the prevention of enzymatic processing of local anesthetics, and is commonly used as an adjuvant in both the perioperative setting and in the ED. Given the relatively low volume and dose of anesthetic that will be administered, we plan to supplement the blocks with 4 mg dexamethasone, divided equally into the three injections.

4.4 End of Study Definition

A participant will have completed this study at 24 to 36 hours after blockade, when the research assistant or performing physician will contact the patient via telephone for follow-up assessment, to evaluate for duration of analgesia. For patients that experience an adverse event that requires admission to the hospital or ambulatory follow-up, their participation in the study might be extended beyond 24 to 36-hours as these adverse events and outcomes will be tracked.

Patients who receive the GNB and rate their pain on the NRS before and after the procedure, even those who refuse the APS-POQ-RED survey responses and who are not available to be reached by phone the next day, will still be included in the data analysis for the primary and one secondary endpoint (pain levels, LOS).

5 STUDY POPULATION

5.1 Inclusion Criteria

To be eligible to participate in this study, an individual must meet all the following criteria:

1. Patient presenting to ED with atraumatic knee pain
2. Provision of signed and dated informed consent form and stated willingness to comply with all study procedures and availability for the duration of the study
3. Equal to or over the age of 18 years
4. Have plain film radiography of the knee obtained during the encounter
5. Pain measured on NRS between 5 and 10

5.2 Exclusion Criteria

An individual who meets any of the following criteria will be excluded from participation in this study:

1. Fracture or dislocation on plain film imaging
2. Large knee joint effusion identified on plain film imaging
3. Allergy to bupivacaine or local anesthetics, contraindication to local anesthetics (e.g., G6PD deficiency), or history of LAST after receiving anesthetics.
4. Pregnancy
5. Incarcerated
6. History of ipsilateral partial or total knee arthroplasty (patients with previous knee surgeries that are unrelated to the joint, e.g., arthroscopy, ligamentous repair will be eligible)
7. Clinical or radiographic concern for infection (e.g., septic joint)
8. Hemodynamic instability
9. Altered mental status or inability to consent for the procedure

Justification of selected inclusion and exclusion criteria:

- Large knee effusion on x-ray: Patients with large knee effusions will not be included in the study as large effusions can make the GNB more difficult to perform by distorting the anatomical and sonographic landmarks, and we wish to avoid the additional risk of inadvertent intra-articular injections. In our experience, we have been able to perform the GNB on patients with small and moderate sized effusions without difficulty. Given that many patients with knee OA and chronic knee pain have small to moderate knee

effusions, including them in this study would provide a more accurate representation of the population suffering with chronic and acute or chronic knee pain.

- Patients <18 years old: pediatric patients typically do not suffer from knee OA
- Pregnant patients have decreased levels of alpha-1 glycoprotein which places them at inherently increased risk for LAST.
- Incarcerated patients will be difficult to follow up with and we will not be able to obtain 2 of the 3 secondary endpoints on these patients.

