1 STUDY SUMMARY

1.1 Synopsis

Title: Ultrasound-Guided Genicular Nerve Block for Knee Pain in the Emergency Department: A Randomized Controlled Trial

Short Title: Genicular Block for Knee Pain: An RCT

Study Description: Patients who present to the emergency department (ED) at any of the clinical sites of the University of Pennsylvania Health System with atraumatic knee pain will be considered for enrollment to be randomized to receive an ultrasound-guided genicular nerve block (GNB) or conventional analgesia. Patients randomized to the intervention arm will receive a three-point GNB with weight-based dosing 0.5% bupivacaine augmented with 4 mg dexamethasone, divided into three separate aliquots to be injected around the superomedial genicular nerve (SMGN), superolateral genicular nerve (SLGN), and inferomedial genicular nerve (IMGN). This will be an open-labeled, investigator-initiated study with convenience enrollment.

Objectives: Primary Objective:

- To determine whether patients receiving a GNB for knee pain experience greater pain reduction compared to conventional analgesia

Secondary Objectives:

- To determine whether patients who receive a GNB experience a longer duration of analgesia compared to those who receive conventional analgesia
- To determine whether patients who receive a GNB report higher patient satisfaction compared to those who receive conventional analgesia
- To determine whether patients who receive a GNB have shorter ED length of stay (LOS) compared to those who receive conventional analgesia

Primary Endpoint:

- Difference in pain level as measured by NRS at pre-intervention (GNB or conventional analgesia) and at either 1-hour post-enrollment or time of ED discharge, whichever occurs first

Secondary Endpoints:	
• Difference in duration of analgesia, assessed at 24-36 hours post intervention.• Difference in APS-POQ-RED between treatment arms, assessed at either 1-hour post-enrollment or time of ED discharge, whichever occurs first.• Difference in ED LOS between treatment arms, as determined by time from enrollment in study to time of ED discharge.

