Study Population:	
Patients presenting with knee pain at any of the four emergency departments: (1) Hospital of the University of Pennsylvania (HUP), (2) Penn Presbyterian Medical Center (PPMC), (3) Pennsylvania Hospital (PAH), and (4) HUP Cedar (Cedar)
 
All genders, age \geq 18, all demographic groups
 
Moderate to severe knee pain (pain measured on NRS between 5 and 10)
 
Exclusions based on general health status: cognitive impairment / dementia, inability to consent for study procedure
 
Exclusion criteria: pregnant; incarcerated; large knee joint effusion as identified on plain film radiography; acute traumatic etiology for knee pain including fracture, dislocation, or suspected tendonous or ligamentous injury; concern for infection including septic joint, abscess, cellulitis, or sepsis; hemodynamic instability; allergy or contraindication to bupivacaine or any of its components
 
Sample size: 17 patients per treatment arm

Phase:	N/A
Description of Sites/Facilities	
(1) Hospital of the University of Pennsylvania
 
(2) Penn Presbyterian Medical Center
 
(3) Pennsylvania Hospital
 
(4) HUP Cedar

Enrolling Sites:	EDs of the four previously mentioned sites
Description of Study Intervention:	The study intervention is an ultrasound-guided three-point GNB, which involves injection of local anesthetic with adjuvant (ideal bodyweight-dosed bupivacaine 0.5% and dexamethasone 4 mg) around the genicular nerves of the knee. The genicular nerves are a series of four terminal

sensory nerve branches of the femoral nerve that provide sensory innervation to the joint capsule of the knee, thereby providing pain relief without motor blockade or paralysis. See detailed description of the study intervention in Section 6. The comparison control arm involves conventional analgesia for knee pain, which includes oral, intravenous, or topical analgesics (e.g., acetaminophen, non-steroidal anti-inflammatory drugs [NSAIDs], opioids, lidocaine patches, heating or cold packs) and will be determined at the discretion of the primary provider caring for the patient. See detailed description of study control arm in Section 6.

Study Duration: 12-months

[figure not shown]
Participant Duration: 24 to 36-hours

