2.2.2 Assessment for Potential Study Products Drug-Drug, Drug-Device, Device-Device Interactions

Potential interactions of bupivacaine include:

Local Anesthetics: Toxic effects of local anesthetics are additive, such that administration of multiple anesthetics can increase the risk of systemic toxicity if greater than weight-based dosing limit.

Monoamine Oxidase Inhibitors and Tricyclic Antidepressants: Co-administration of bupivacaine with these agents can produce severe, prolonged hypertension if administered systemically.

Ergot-Type Oxytocic Drugs: Co-administration of bupivacaine with these agents can produce severe, prolonged hypertension or cerebrovascular accidents if administered systemically.

Nonselective Beta-Adrenergic Antagonists: Co-administration of bupivacaine with these agents can cause severe hypotension and bradycardia if administered systemically.

Drugs Associated with Methemoglobinemia: Co-administration of bupivacaine with the following classes of agents can increase risk of developing methemoglobinemia: Nitrates (nitric oxide, nitroglycerin, nitroprusside, nitrous oxide), Antineoplastic agents (cyclophosphamide, flutamide, hydroxyurea, ifosfamide, rasburicase), Antibiotics (dapsone, nitrofurantoin, para-aminosalicylic acid, sulfonamides), Antimalarials (chloroquine, primaquine), Anticonvulsants (phenobarbital, phenytoin, sodium valproate).

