2.2.3 Clinical Adverse Event Profile

General Adverse Effects: nausea, vomiting, chills or shivering, headache, back pain, sexual dysfunction, restlessness, anxiety, vertigo

Local Anesthetic Systemic Toxicity (LAST): CNS Reactions (perioral tingling, tongue paresthesia, dizziness, tinnitus, blurry vision, tremors, seizures, myoclonic jerks), Cardiovascular Reactions (cardiovascular collapse, bradycardia, hypotension, cardiac arrest, ventricular arrhythmia)

Allergic Reactions: urticaria, pruritus, erythema, angioneurotic edema (including laryngeal edema), tachycardia, sneezing, nausea, vomiting, dizziness, syncope, excessive sweating, elevated temperature, and severe hypotension

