2.3 Risk/Benefit Assessment

2.3.1 Known Potential Risks

Manufacturer Drug Information:

LAST: As with all local anesthetics, the principal risk of bupivacaine is LAST, as previously described. To mitigate the risk of this, (1) anesthetic will be dosed by ideal body weight to not exceed the limit of safe dosing (e.g., 80% of maximal safe dosing by ideal body weight in patients with BMI greater than or equal to 25 kg/m² and actual body weight in patients with BMI less than 25 kg/m²), (2) anesthetic will be administered slowly to identify any early signs of toxicity, (3) aspiration will be performed prior to each injection to ensure anesthetic will not be administered intravascularly, and (4) real-time ultrasound guidance with color doppler will be performed to visualize blood vessels to ensure anesthetic is not being administered intravascularly. The risk of LAST is extremely low (<1/10,000) ([Neal 2018](#)).

Bleeding: With any percutaneous procedure, there is a risk of superficial and deep tissue bleeding. To minimize this risk, continuous real-time ultrasound visualization of the injection needle will be performed to ensure vasculature is not compromised.

Infection: With any percutaneous procedure, there is a risk of soft tissue infection. To minimize this risk, the skin overlaying the injection sites will be prepped in standard fashion with chlorhexidine, sterile ultrasound probe covers will be used, operators will wear sterile gloves, and single-single use sterile needles will be used for each injection.

Alternative Procedures: Considered using higher concentrations (0.75%), and while these have been proven safe for peripheral use, we elected to proceed with lower concentration (0.5%) for safety. Preliminary (non-published) data suggests that weight-based dosing of 0.5% bupivacaine can produce desired anesthesia. We will use ultrasound-guidance rather than landmark-guidance to visualize and avoid the genicular arteries that lay in proximity to the genicular nerves ([Callese 2023](#)).

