6.5 Concomitant Therapy

For the GNB arm, in addition to bupivacaine, the GNB will be augmented with adjuvant dexamethasone (4 mg divided into three aliquots). Dexamethasone is commonly used in the

perioperative setting by regional anesthesiologists and in the ED to extend the duration of regional anesthesia ([Fernández Martin 2023](#)).

6.5.1 *Rescue Medicine*

For the GNB arm, if signs or symptoms of LAST were to develop at any point during administration of the intervention drug or after administration, patients will be assessed for the need for rescue medications. At all study sites, benzodiazepines and lipid emulsion therapy will be available and administered if deemed necessary by the performing physician ([Shalaby 2024](#)). For seizures, a benzodiazepine such as midazolam or lorazepam will be administered as per established dosing guidelines. Intralipid will be administered as per institutional guidelines to help reverse LAST. The date and time of rescue medication administration as well as the name and dosage regimen of the rescue medication will be recorded.

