8.3.4.2 Relationship to Study Intervention

All adverse events (AEs) must have their relationship to <study intervention> assessed by the clinician who examines and evaluates the participant based on temporal relationship and his/her clinical judgment. The degree of certainty about causality will be graded using the categories below. In a clinical trial, the study product must always be considered.

- Related – The AE is known to occur with the GNB, there is a reasonable possibility that the GNB caused the AE, or there is a temporal relationship between the GNB and event.

Reasonable possibility means that there is evidence to suggest a causal relationship between the GNB and the AE.

- Not Related – There is no temporal relationship between the GNB and event onset, or an alternate etiology has been established.

8.3.4.3 *Expectedness*

The medical director, [name], will be responsible for determining whether an adverse event (AE) is expected or unexpected. An AE will be considered unexpected if the nature, severity, or frequency of the event is not consistent with the risk information previously described for the GNB.

8.3.5 *Time Period and Frequency for Event Assessment and Follow-Up*

Safety will be assessed by monitoring and recording potential adverse effects using the Common Terminology Criteria for Adverse Events (CTCAE) at each study visit. Participants will be monitored by medical histories, physical examinations, and vital signs. If CTCAE grading does not exist for an adverse event, the severity of mild, moderate, severe, life-threatening, and death, corresponding to Grades 1-5, will be used whenever possible.

At each contact with the subject, the investigator will seek information on adverse events by non-directive questioning and, as appropriate, by examination. Adverse events may also be detected when they are volunteered by the subject during the screening process or between visits, or through physical examination, laboratory test, or other assessments. Information on all adverse events will be recorded in the source documentation. To the extent possible, adverse events will be recorded as a diagnosis and symptoms used to make the diagnosis recorded within the diagnosis event.

As much as possible, each adverse event or follow-up information will be evaluated to determine:

1. Severity grade (CTCAE Grade 1-5)
2. Duration (start and end dates)

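### Every nerve block contains dexamethasone, but the drug exclusion covers only bupivacaine and local anesthetics, so as written a patient allergic to dexamethasone is eligible

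*Protocol*

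**What the plan says.** The synopsis (Protocol 1.1) describes the block as "weight-based dosing 0.5% bupivacaine augmented with 4 mg dexamethasone, divided into three separate aliquots". Section 6.5 repeats that "the GNB will be augmented with adjuvant dexamethasone (4 mg divided into three aliquots". Sections 4.3 (dose justification), 6.2.4 (preparation) and 7.1 (discontinuation) also include dexamethasone, and none of them makes it optional.

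The drug-related exclusion appears twice:

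- Section 5.2, criterion 3: "Allergy to bupivacaine or local anesthetics, contraindication to local anesthetics (e.g., G6PD deficiency), or history of LAST after receiving anesthetics".
- Synopsis: "allergy or contraindication to bupivacaine or any of its components".

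The background text on drug risk is written around the anesthetic. Section 2.2.2 opens with "Potential interactions of bupivacaine include" and lists nothing for dexamethasone. Section 2.3.1 states that "the principal risk of bupivacaine is LAST, as previously described", then turns to bleeding and infection as risks of the needle procedure. Section 2.2.3 lists general effects, systemic toxicity of local anesthetics, and allergic reactions.

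Under section 8.3.4.3, an adverse event is unexpected if it "is not consistent with the risk information previously described for the GNB". Section 8.3.5, item 4, applies a similar test against the investigator brochure, if there is one, or the protocol.

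**The concern.** Eligibility and risk text should cover everything that is injected. Here they cover one of two drugs.

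The written list matters because of who uses it. Under section 4.1, a research assistant or the performing physician screens for eligibility, a research assistant may take consent, and the physician doing the block need not be the one treating the patient. A screener who follows section 5.2 to the letter has no instruction to ask about dexamethasone.

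Two things are at stake. The first is safety: a patient with a known allergy to part of the injectate can be randomized to receive it. The second is the comparison: if the problem is noticed later, it is noticed in one arm only, after allocation, whereas an exclusion applied at screening acts equally on both arms. A lesser matter is that the reference text for judging expectedness is incomplete for one of the two drugs.

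**Working it through.** No formula applies, and the plan states no figure on this point. The check sets the sections side by side.

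1. **What is injected.** The synopsis and sections 4.1, 4.3, 6.1.2, 6.2.4 and 6.5 all give bupivacaine plus 4 mg dexamethasone, and section 7.1 names both drugs as making up the block. Section 6.1.1 prints the dexamethasone amount in mL rather than mg. That is a separate inconsistency to be reconciled, but it too puts the steroid in the block.

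2. **What the exclusion reaches.** Criterion 3 of section 5.2 names bupivacaine and local anesthetics. The synopsis adds the components of bupivacaine. Under section 6.2.2, dexamethasone is a separate product mixed in at the bedside, so it is not a component of bupivacaine. The drug exclusion is stated in 2 places, and 0 of them reach dexamethasone.

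3. **Applying the rules to a test patient.** Take an adult with atraumatic knee pain, an NRS score in range, a film without fracture or large effusion, and a known dexamethasone allergy. All five inclusion criteria can be met. The other exclusions (fracture or dislocation, large effusion, pregnancy, incarceration, ipsilateral arthroplasty, infection, hemodynamic instability, altered mental status) do not apply. The patient is eligible.

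4. **When a later check would act.** Sections 4.1 and 8.1 give the order: screening, consent, baseline NRS, randomization, treatment. Under section 6.2.1, the physician orders both drugs for the GNB arm and a pharmacist approves them. That step follows allocation and exists for these drugs only in the GNB arm. A refusal there leaves a randomized patient either without the assigned block (a missed treatment) or with a block that omits the adjuvant (a protocol deviation).

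5. **Expectedness.** Sections 2.2.1 to 2.3.3 never name dexamethasone. The only risk text that does is on crystallization of the mixture, in section 6.2.3, and the protocol treats that as having no clinical consequence.
   - *Allergic events:* section 2.2.3 gives "Allergic Reactions: urticaria, pruritus, erythema, angioneurotic edema (including laryngeal edema), tachycardia" and further signs without naming a drug, so such an event after the block may count as already described.
   - *Non-allergic events specific to the steroid:* if they are not on the general list in section 2.2.3, they have no counterpart in the protocol and could be classed as unexpected under 8.3.4.3 and 8.3.5.

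6. **Size.** The protocol gives no frequency for dexamethasone allergy, so no expected count can be computed. For scale only, one patient in an arm of 17 is 1/17 = 5.9% of that arm. This is the weight of any single patient, not an estimate of how many are affected.

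**The case against.** The best defense is that practice would catch this. Section 6.1.1 says the drugs are used within their labeling, a physician orders them, and a pharmacist approves the order. The consent process in section 10.1.1 covers the block and its risks, so a patient who knows of an allergy might raise it. All this makes an actual injection into an allergic patient less likely. It does not change eligibility, and the ordering safeguards act after randomization in one arm. The consent pages are not available for review, so what they say about dexamethasone cannot be checked.

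It can also be said that this is an omission rather than a contradiction, and that choosing contraindications is clinical business. The second part stands: the list is for the sponsor to set. The first part does not remove the point, because following the stated rule admits a patient whom the described injectate would expose.

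A reader might infer more than the documents support:

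- **That any dexamethasone reaction is unexpected by rule.** This fails for allergic reactions, since the list in section 2.2.3 is not tied to a drug.
- **That 48-hour reporting as an unanticipated problem follows.** Section 8.4.1 requires all three of its criteria, including a suggestion of greater risk than was already known. An unexpected label alone is not enough, and the first criterion also refers to the consent document. Reporting of serious events under section 8.3.7 does not depend on expectedness.
- **That all 17 GNB patients are affected.** Only a patient with a dexamethasone allergy or contraindication, or with a steroid-specific event outside the listed effects, is touched.
- **That withholding the adjuvant is crossover.** A patient given the block without dexamethasone has still had a genicular block.

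**Conclusion.** The gap is real and narrow. The exclusion wording covers one of the two drugs in every block, and a patient with a known dexamethasone allergy passes the criteria as written. Existing checks could intervene only after randomization and only in the GNB arm. The expectedness point holds only for steroid-specific, non-allergic events missing from section 2.2.3, and only in the sense that they could be classed as unexpected.

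The number of affected patients cannot be derived and may be zero. Sample size, power and alpha do not depend on it. The conclusion assumes that the block always includes dexamethasone, as every description of it implies, and that screeners apply sections 5.1 and 5.2 as printed. The change is worth making because it is cheap and bears on safety, not because a measurable bias has been shown.

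**What to change.** Reconcile the exclusion wording in the synopsis and section 5.2 with the two-drug injectate, so that screening before randomization considers both drugs. Reconcile the interaction, adverse event and risk text (sections 2.2.2, 2.2.3 and 2.3.1) in the same way, so that the expectedness tests in 8.3.4.3 and 8.3.5 have a reference for both. It would help if section 2.2.3 said which drug or drugs each list refers to. The specific contraindications and risks are for the sponsor to set; none is proposed here.

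The cost is a short amendment to one criterion (stated in two places) and three background sections, and possibly a few more screen failures.
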